3.2 Secondary outcomes

The secondary outcomes will be :

- To evaluate the diagnostic accuracy and reproducibility of the ultrasound score in the diagnosis of swallowing disorders
- To evaluate the reproducibility and diagnostic accuracy of hyoid bone ascension in the diagnosis of swallowing disorders
- To evaluate the reproducibility and diagnostic accuracy of the digastric muscle thickening fraction in the diagnosis of swallowing disorders
- To evaluate the reproducibility and diagnostic accuracy of the genohyoid thickening fraction in the diagnosis of swallowing disorders
- To evaluate the reproducibility and diagnostic accuracy of the amount and duration of lingual movement in the diagnosis of swallowing disorders

4 Eligibility criteria

4.1 Inclusion criteria

Patients with the following criteria will be included:

- Patients admitted to the day hospital ;
- Patients with a medical indication for videofluoroscopy ;
- Medical prescription for physiotherapy assessment ;
- Ultrasound operator available;
- Patient at least 18 years old at the time of inclusion;
- Affiliation with a social security scheme or beneficiary of such a scheme ;
- Oral, free, informed and express consent of the patient.

4.2 Non-inclusion criteria

Patients with the following criteria will not be included:

- Patient with total laryngectomy ;
- Patient's refusal to participate in the study ;
- Known pregnancy ;
- Person subject to a legal protection measure ;
- Cognitive impairment incompatible with understanding instructions;
- Patient under guardianship or curatorship ;
- Patient in care limitation.

4.3 Recruitment procedures

Patients will be recruited prospectively and consecutively in the HDJ Déglutition of the Forcilles Hospital, the only inclusion centre. The doctor in charge of the unit identifies the patients during the initial consultation.

The number of annual admissions is 108 patients. The monthly recruitment target is 4 patients.

[figure not shown]
5 Research design

5.1 Type of study

This is a prospective, monocentric, interventional cohort study with minimal risks and constraints falling within the scope of article L.1121-1 of the Public Health Code.

The research will be conducted in accordance with the protocol.

5.2 Research scheme

5.3 Provisional research timetable

The recruitment period will be 25 months with a half-day follow-up of patients, for a total estimated study duration of 25 months.

- Submission to IRB: November 2020
- Start of inclusions: January 2021
- Duration of the inclusion period: 25 months
- Duration of each patient's participation: half a day
- End of inclusions: February 2023
- Total duration of the research: 25 months
- Communication in congresses: Société de Réanimation de Langue Française ; Congrès de Pneumologie de Langue Française ; Journées Francophones en Kinésithérapie ; Association de Rééducation Oro-Maxillofaciale ; SEPAR ;
- Publication: July 2023

5.4 Location of the study

The study will take place at the Forcilles Hospital, in the HDJ dedicated to the evaluation of swallowing disorders.

6 Description of the usual care in HDJ deglutition

6.1 Description of the usual course of the HDJ

A total of three patients can be admitted each week in this HDJ, one patient per half-day in each of the three half-days dedicated to it. This HDJ lasts approximately three hours and starts with the reception of the patient by the nurse and continues with :

- Clinical examination and swallowing test (physiotherapist and speech therapist) ;
- Nasofibroscopy (ENT doctor) ;
- Videofluoroscopy (radiologist) ;
- Dietetic consultation (dietician) ;
- Medical consultation (delivery of the hospital report).

After all investigations have been carried out and before the dietetic consultation, a consultation meeting is held between the doctor, the speech therapist and the dietician of the unit. This meeting allows the therapeutic strategy and any necessary adaptations to be defined.

After the meeting, the dietician receives the patient in consultation and informs him/her of the recommendations necessary to maintain or recover a satisfactory nutritional status, while following the adaptations of the mode of feeding possibly decided in the consultation meeting. Finally, the patient is received by the doctor in charge of the unit who gives him the hospitalization report.

All examinations and consultations are carried out within the usual framework of the HDJ Déglutition and are systematically prescribed by the doctor in charge.

6.2 Standard assessment procedures

6.2.1 Clinical examination of swallowing

The speech and language therapist studies the patient's medical file and takes note of the reason for hospitalisation (and possibly of the swallowing disorder assessments and treatments carried out previously). The SLT then carries out a clinical assessment of the patient.

This assessment consists of two parts: the clinical examination and the swallowing test.

This examination consists mainly of observation and palpation of the different structures at rest and during active movements (praxis) and counter-resistance requested by the speech therapist. This allows the evaluation of :

- The tone and mobility of the lips, tongue, cheeks, soft palate and temporomandibular joints;
- Reflex and airway protection mechanisms;

- Cranial pairs involved in swallowing and the oro-maxillofacial sphere;
- Posture and motor control of the head, cervical spine and upper limbs.

Following these investigations, swallowing trials with different textures are routinely performed.(28) The speech and language therapist will look for signs of swallowing disorders such as coughing or voice changes.

6.2.2 Videofluoroscopy

This examination takes place in the radiology department of the Forcilles Hospital. It is the last examination performed by the patient. The electro-radiology manipulator (MER) carries out the examination on the prescription and under the supervision of the radiologist, as defined by the legal framework for this examination. The speech therapist is present to collect information useful for the assessment and the possible proposal of rehabilitation. Swallowing tests with different textures and quantities are carried out. The details of the order of the swallowing tests, the textures and quantities used are described in **Annex 3**.

7 Evaluation procedure added by the research

A swallowing ultrasound will be added as part of the research.

7.1 Operator training in ultrasound

The ultrasound examination will be performed by a physiotherapist, blind to the totality of the examinations performed on the patient. The details of the ultrasound examination carried out within the framework of the protocol can be found in **appendix 4**.

The operator training is as follows:

- 3 days of theoretical and practical training;
- More than 100 ultrasounds supervised by a radiologist;
- Two years of independent practice.

Similarly, all the physiotherapists performing the ultrasound scans are already involved in other research projects using lung, diaphragm and peripheral muscle ultrasound:

<https://clinicaltrials.gov/ct2/show/NCT02474797>,

<https://clinicaltrials.gov/ct2/show/NCT02881814>

and

<https://clinicaltrials.gov/ct2/show/NCT04373811>

7.2 Practical details of the ultrasound examination

The examination, the details of which can be found in **Appendix 4**, is carried out using a Sonoscape Expert 2 ultrasound scanner (Digital Color Doppler Ultrasound System; Sonoscape medical corp. China) equipped with a linear probe (7-10 MHZ) and a convex probe (3-5 MHZ). Both probes will be used for each of the swallowing trials.

In order to assess inter- and intra-examiner reliability, the tests will be performed by two different operators and twice by the same operator, i.e. 3 identical examinations in total, in the first 20 patients included.

The duration of an examination will not exceed 15 minutes, i.e. a total duration of the ultrasound examination of 45 minutes for the first 20 patients (15 minutes for examination, 3 examinations).

The patient is in a sitting position and performs salivary swallowing attempts on request of the operator.

The convex probe will be placed under the chin, in the sagittal plane and between the edges of the hyoid bone and the mandible. The acoustic shadows of these bones will allow us to localise the structures and centre the image. (53)(54)

The following elements will be assessed:

- The position of the hyoid bone at rest and during swallowing;
- The thickness of the geniohyoid at rest and during swallowing;
- The contractility of the tongue ;
- The duration of contraction of the geniohyoid ;
- The number of swallowing attempts.

The linear probe will also be placed submentally, along a transverse axis, in order to qualitatively and quantitatively evaluate the suprahyoid muscles (55)

Qualitative analysis will be performed using the Heckmatt Score. (56) Quantitative analysis will be performed by measuring the thickness of the muscles at rest and during contraction. These two measurements will be used to calculate its thickening fraction. The thickness of the muscle is calculated by quantifying the distance between the upper and lower fascia of the muscle.

7.3 Semiology in aerodigestive tract ultrasound

The different dysfunctions of the structures or functions involved in swallowing can be defined on ultrasound by the following signs

- (1) Lingual dysfunction (53)(57)(54):
 - a. Abnormal movement pattern ;
 - b. Several attempts identified;
 - c. Decreased range of motion ;
 - d. Decrease in thickness.
- (2) Suprahyoid muscle dysfunction (58)(59) :
 - a. Decrease in signal strength ;
 - b. Fat invasion and poorly defined muscle boundaries;
 - c. Decrease in thickness or surface area compared to contralateral ;
 - d. Decreased mobility and thickening fraction compared to contralateral.
- (3) Genohyoid dysfunction (55)(60) :
 - a. Decreased thickening fraction.
- (4) Laryngeal ascension defect (60)(58) :
 - a. Ascension <1.5cm. measured indirectly by assessment of hyoid bone ascension.

8 Conduct of the research

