9.3 Potential variables of the ultrasound score

Structures assessed		Results	Weighting
Language			
	Abnormal movement	Yes/No	
	> 1 attempt identified	Yes/No	
	Range of motion	< threshold > threshold (only to be defined)	
	Thickness	< threshold > threshold (threshold to be defined)	
Suprahyoid muscles			
	Signal strength (Heckmatt score)	1-4	
	Poorly defined fat involution and muscle boundaries	Yes/No	
	Decreased surface area compared to contralateral	Surface < threshold (threshold to be defined)	
	Thickening fraction compared to contralateral	< threshold > threshold (only to be defined)	
Geniohyoid			
	Decreased thickening fraction	< threshold > threshold (only to be defined)	
Laryngeal ascension			
	Ascension measured indirectly by assessment of hyoid bone ascension	< threshold > threshold (only to be defined)	

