9.4 Determination of classes and thresholds of quantitative variables

The hypothesis of a linear relationship between the logit of the diagnosis of swallowing disorders objectified by VFSS and the quantitative variable will be tested. If it is verified, the variable will be dichotomised. The threshold used will be determined using ROC (Receiver

Operating Characteristic) curve analysis, which will allow the threshold for which sensitivity and specificity are maximum to be retained. (62)

The variables for which the hypothesis is not verified will be split into classes. (63)

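### Hyoid ascension has a 1.5 cm limit in 7.3 but an open, ROC-derived threshold in 9.3 and 9.4; the plan does not say which cut-off its stand-alone accuracy outcome uses, and does not correct for optimism

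*Combined protocol and SAP*

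**What the plan says.** - **Section 7.3** introduces its list with "The different dysfunctions of the structures or functions involved in swallowing can be defined on ultrasound by the following signs". For laryngeal ascension the sign is "Ascension <1.5cm. measured indirectly by assessment of hyoid bone ascension". It is the only sign in that list with a limit in measured units; the other quantitative signs speak only of a decrease.
- **Section 9.3** lists a candidate variable in nearly the same words, "Ascension measured indirectly by assessment of hyoid bone ascension", with the result coded as "< threshold > threshold (only to be defined". The tongue-thickness row of the same table shows that this means a threshold to be defined. The 1.5 cm is not carried over.
- **Section 9.4** tests linearity between each quantitative variable and the logit of the VFSS diagnosis. "If it is verified, the variable will be dichotomised", using ROC analysis and retaining "the threshold for which sensitivity and specificity are maximum to be retained". In the other branch, "The variables for which the hypothesis is not verified will be split into classes", and no class limits are given.
- **Sections 2.2 and 3.2** make the reproducibility and diagnostic accuracy of hyoid ascension, separately from the score, a secondary objective and outcome.
- **Section 9.7.2** describes a ROC threshold and accuracy measures for the score only. Section 9.7 mentions no split sample, cross-validation or bootstrap.

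**The concern.** One measurement is treated in two ways, and nothing links them. For the stand-alone hyoid outcome, an analyst could use 1.5 cm, a ROC-derived cut-off or classes, and could choose after seeing the results.

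The options differ statistically. A cut-off chosen to maximise sensitivity and specificity in a sample, and then evaluated in that same sample, looks better than it will in new patients. A cut-off fixed before the data does not have that problem. Hyoid ascension is the one quantitative variable for which the protocol already states such a limit, so an estimate free of threshold-selection optimism is within reach for a named secondary outcome.

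**Working it through.** **Inputs from the documents.** Five variables, 10 events per variable and 50% prevalence (9.1). The cut-off rule is maximum sensitivity and specificity (9.4), taken here as the maximum of Youden's J = sensitivity + specificity − 1. There is a single cohort, with no validation set and no optimism correction (9.7).

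**The plan's own figure.** N = variables × events per variable / prevalence = 5 × 10 / 0.50 = 100, which reproduces 9.1. It implies 100 × 0.50 = 50 positive and 50 negative patients.

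**Inputs that are assumptions.** The documents give no accuracy figure and no distribution for hyoid ascension. I assumed normal values with equal variance in the two groups, δ standard deviations apart, so AUC = Φ(δ/√2) and the best attainable J is 2Φ(δ/2) − 1. For δ = 1, AUC = 0.76 and the best J = 2 × 0.6915 − 1 = 0.383.

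**Simulation.** Each of 4,000 simulated studies per setting has 100 patients. The cut-off is placed at the highest in-sample J. Apparent J at that cut-off is compared with the true J of the same cut-off; the difference is the optimism. With 50 v 50 patients:

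| AUC | Apparent J | True J | Optimism |
|---|---|---|---|
| 0.5 | 0.116 | 0.000 | 0.116 |
| 0.6 | 0.231 | 0.124 | 0.107 |
| 0.7 | 0.360 | 0.268 | 0.092 |
| 0.8 | 0.508 | 0.428 | 0.080 |
| 0.9 | 0.683 | 0.618 | 0.066 |

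Separate runs with the groups 0.5, 1.0 and 1.5 SD apart (AUC 0.64, 0.76 and 0.86) gave about 10, 8.4 to 8.7, and 7.3 to 7.6 points. Hence the range of 7 to 10 points on the sum, or roughly 4 to 5 on each measure. If prevalence also varies from 30% to 80% over AUC 0.5 to 0.9, the range widens to 6.6 to 14.5 points.

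Only the sum is tabulated. Nearly half of the simulated samples have tied optimal cut-offs, so the split between sensitivity and specificity depends on how ties are broken.

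**Cut-off fixed in advance.** Mean estimated J equals true J within simulation error:
- AUC 0.7: 0.288 v 0.289.
- AUC 0.8: 0.448 v 0.448.
- AUC 0.7 with the cut-off 1 SD away from the optimum: 0.181 v 0.179. Accuracy is lower here, but it is estimated without selection optimism.

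**Bootstrap correction.** Re-selecting the cut-off in each resample and subtracting the estimated optimism leaves about 2 to 4 points of overstatement. It removes most of the optimism, not all.

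**The case against.** **7.3 is descriptive.** It is a section on semiology and describes when one function is deficient. Section 9.4 seeks a threshold for a different target, any swallowing disorder on VFSS, and Appendix 3 lists a laryngeal ascension defect as only one of 12 mechanisms. A sign of one mechanism and a diagnostic cut-off for the whole disorder can coexist. This stands: the two sections are unreconciled rather than flatly contradictory.

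**No biased figure is actually promised.** A reader might infer that the plan discards 1.5 cm and commits to reporting hyoid accuracy at an optimised cut-off in the same patients. The documents do not say so. Sections 9.3 and 9.4 concern building the score, 9.7.2 concerns the score, and the ROC rule applies only if linearity is verified. What is supported is an unspecified threshold. The optimism follows only if the 9.4 cut-off is carried into the stand-alone outcome. The class branch does not settle the matter, because its limits are unstated too.

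**Deriving thresholds is an aim.** Section 1.3.3 criticises earlier studies for not usually defining a diagnostic threshold. The basis of 1.5 cm lies in cited sources that cannot be checked here, including whether it suits a hyoid measurement during the salivary swallows of 7.2. A badly placed fixed cut-off has a price: at AUC 0.7 and 1 SD off the optimum, true J is 0.179, against 0.268 for the ROC-chosen cut-off. This also stands. It argues for reporting 1.5 cm beside the ROC-derived cut-off, not for making it the headline.

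**The optimism is small beside sampling error.** For a sensitivity of 70% in 50 patients, the 95% CI half-width is 1.96 × √(0.70 × 0.30 / 50) = 0.127, about 13 points, and 9.2 promises CIs. That is fair as to scale. But optimism shifts the estimate in one direction, and an ordinary CI does not allow for it.

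**The wider gap is elsewhere.** The other data-derived thresholds, the AIC selection and the score cut-off are uncorrected as well, and settling the hyoid limit does not cure them. This is true, but it does not remove the question for this outcome.

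**Conclusion.** The point holds as a low-severity improvement. The plan states a limit for hyoid ascension in 7.3, leaves the threshold for the same measurement open in 9.3, and does not say which cut-off the secondary outcome in 3.2 uses. If the 9.4 ROC cut-off is used and evaluated in the same patients, sensitivity plus specificity is overstated by about 7 to 10 points in total. The exact size rests on the assumed 50 v 50 split, normal values with equal variance and AUC 0.64 to 0.86. The direction was the same in every setting tried.

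It would go too far to call the accuracy at 1.5 cm unbiased. A pre-fixed limit removes threshold-selection optimism only. Excluding patients whose videofluoroscopy could not be completed (Appendix 3), and the unstated rule for a positive VFSS (9.5), would affect that estimate as well. Nor do the documents show that 1.5 cm is the better limit; which limit is clinically right is for the sponsor.

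**What to change.** 1. Reconcile 7.3 with 9.3 and 9.4 by stating whether 1.5 cm has a role in the analysis or is descriptive only.
2. For the hyoid secondary outcome, pre-specify in 9.4 or 9.7.2 sensitivity and specificity with 95% CIs at the 1.5 cm already in 7.3.
3. Alongside, report accuracy at the ROC-derived cut-off, corrected by bootstrap with the cut-off re-selected in every resample. Label it as data-derived, since some optimism may remain.

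**Cost.** A sentence or two of text, one extra two-by-two table and a short bootstrap routine in R, which 9.2 already names. There are no new data, and N stays at 100. The corrected figure will look slightly less favourable, and accuracy at 1.5 cm may be lower if that limit lies far from the optimum.

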8.1 Pre-inclusion visit

8.1.1 Checking inclusion and non-inclusion criteria

When a patient is admitted to the HDJ, the doctor in charge of the unit checks the presence of the inclusion criteria and the absence of the non-inclusion criteria in the medical file sent to him by the doctor referring the patient and in the patient's computerised file, if applicable.

8.1.2 Patient information and consent

When all the criteria allow the inclusion of the patient, the investigating physician informs the patient of the purpose of the study during a consultation. He/she provides the patient with all the information described in the information note (**appendix 5**) and, if necessary, obtains the patient's free, informed and express oral consent. This consent will be recorded in the patient's computerised medical record.

8.2 Inclusion visit

The inclusion visit takes place when the patient agrees to participate in the study. The following data will be collected:

- (1) Basic data :
 - a. Age, gender, height, weight ;
 - b. Medical history :
 - i. Oral language disorders ;
 - ii. Stay in intensive care: indicate if the patient required mechanical ventilation, tracheotomy, nasogastric tube;
 - iii. Neurological alterations/diseases: previous stroke; Parkinson's; ALS; dementia;
 - iv. Cervical, ENT or oesophageal surgery, (attach surgical report) ;
 - v. Orthodontic treatment.
- (2) Information on nutritional status ;
- (3) Presence or absence of a tracheostomy at the time of the examination;
- (4) Presence or absence of a nasogastric tube at the time of the examination ;

(5) Data on care :

- a. Professional who requested hospitalization ;
- b. Diagnostic hypothesis of the referring clinician ;
- c. Information on the management of swallowing disorders ;
- d. Dietary adaptations.

8.3 Visit of the ultrasound operator

The ultrasound examination is the first examination performed in order to maintain the operator's ultrasound blindness. It will take place in the consultation room provided in the HDJ.

8.4 Visit from the speech therapist

This visit takes place following the ultrasound examination. Before the visit and the clinical examination, the speech and language therapist will read the patient's medical file. The SLT then carries out the clinical examination in the usual way.

8.5 Performing imaging tests

Imaging examinations will take place after the ultrasound examination and the SLT visit. They will be carried out in accordance with the procedure described in **Appendix 3**. After the imaging tests have been carried out and depending on the results, the speech and language therapist will adapt the advice on food textures to the patient.

Following this examination and taking into account the results of the various investigations carried out during the day, the speech and language therapist will summarise the assessment and choose the dietary adaptations. The degree of severity corresponding to the DOSS scale, details of which are given in **Appendix 1**, will be noted in the observation booklet.

8.6 End of research visit

This visit takes place during the end-of-day consultation. It is carried out by the doctor in charge of the unit, who gives the patient the hospitalization report and ensures the transcription of the information in the research observation book.

8.7 Summary table

	Pre-inclusion	Inclusion	Visit of the ultrasound operator	Visit from the speech therapist	Performing imaging tests
Information for the patient or relative	✓				
Collection of basic data (age, sex, BMI, medical history)		✓			
Collection of the reason for hospitalisation in HDJ		✓			
Collection of information on medical and rehabilitation care		✓			
Clinical examination				✓	
Ultrasound examination			✓		
VFSS					✓
DOSS and PASS information					✓

9 Statistical aspects

